8.9.6 Nursing Implications

1. GI toxicities leading to alteration in nutritional status. Patients require daily mouth care regimen which may include narcotic analgesic and potentially parenteral nutrition.
2. Painful desquamation may require local care and narcotic analgesics.

8.10 Antithymocyte Globulin (Rabbit) (Thymoglobulin®; rabbit ATG)

8.10.1 Availability

Antithymocyte globulin is commercially available as a lyophilized powder for reconstitution containing 25 mg per vial. Each vial of powder is supplied with 5 mL diluent.

8.10.2 Storage & Stability

Intact vials should be stored under refrigeration and protected from light. Do not freeze. Reconstituted solutions should be used within 4 hours. Further diluted solutions for infusion should be used immediately after dilution.

8.10.3 Preparation

Remove the ATG rabbit plus diluent from the refrigerator and allow them to reach room temperature prior to reconstitution. Reconstitute each 25 mg vial with 5 mL of the diluent provided (sterile water for injection, USP). Rotate the vial gently to dissolve the powder. The resultant solution contains 5 mg/mL of ATG rabbit. Withdraw the calculate dose and inject into D₅W or NS for IV infusion. The final

concentration should be 0.5 mg/mL. The solution should be administered through a 0.22 micron filter.

8.10.4 Administration

ATG rabbit will be administered IV at a dose of 2.5 mg/kg/day for 3 days (on Days -4, -3, and -2). The first dose should be infused over at least six hours, and subsequent doses over at least 4 hours. Infuse through a 0.22 micron in-line filter. Acetaminophen 650 mg PO, diphenhydramine 25-50 mg PO/IV, and methylprednisolone 1 mg/kg IV should be administered at the initiation and midway through each antithymocyte globulin (rabbit) infusion to minimize infusion reactions.

8.10.5 Toxicity

Infusion reactions such as fever and chills are common, occurring in more than 10% of patients. Steroids, antihistamines and acetaminophen will be given, as described above, to minimize infusion reactions. Hypersensitivity reactions, including anaphylaxis, occur less frequently and may also be minimized with steroids and antihistamines.

Immunosuppression from antithymocyte globulin (rabbit) is associated with an increase in opportunistic infections, including fungal, viral, and pneumocystis infections.

Rev. 2/13 **9. Statistical Considerations**

Rev. Add10 **9.1 Original Design Overview**

Rev. 2/12 In this study, 747 patients will be stratified by age (60 to 69 vs. over 70), therapy-related AML, and the presence of AHD (antecedent hematologic disorder) at the time of diagnosis of AML, then randomized to receive either the standard therapy induction treatment or clofarabine induction treatment. If achieving CR or CRI, these patients will continue to receive standard or clofarabine consolidation treatments. Patients who have a matched sibling donor and who achieve a 'morphologic leukemia-free state' will undergo non-myeloablative allogeneic transplant. For the patients who do not undergo non-myeloablative allogeneic transplant, after receiving the induction and consolidation therapies, if patients are still in CR or CRI, they will be randomized to receive either decitabine maintenance treatment or observation, stratified on the induction and consolidation therapy, cytogenetics and age. We anticipate that approximately 8% of patients will undergo allogenic transplant. We assume 25% of patients who do not receive allogenic transplant go through the second randomization.

The primary objective of this trial is to determine the effect of clofarabine on overall survival (OS) in comparison with standard therapy (daunorubicin & cytarabine in induction and cytarabine in consolidation) in newly-diagnosed AML patients with age over 60 years. Since clofarabine is believed to be less toxic and also clofarabine is expected to prolong OS, a non-inferiority design with superiority alternative is preferred. If clofarabine turns out to be non-inferior to the standard therapy, the superiority of clofarabine will be tested. Another main endpoint of interest in this study is the 30-day mortality rate. It is suspected that clofarabine has a lower early mortality rate. The 30-day mortality rate will be tested after the inferiority of overall survival of clofarabine is rejected. The non-inferiority test of OS, the superiority test of OS and the mortality endpoints fit into a hierarchical framework, since the superiority test of OS and the mortality endpoint will both be tested only conditional on inferiority of OS being rejected. Therefore, non-inferiority of OS will be tested at a one-sided 0.025 level, and superiority of OS and 30 day mortality rate will both be tested at a nominal level of 0.0125 (one-sided). The overall type I error rate of all three tests is still controlled at 0.025.

Rev. 2/12 As one of secondary endpoints, the induction complete response (CR) rates between clofarabine arm and the standard treatment arm will be compared. A non-inferiority test with superiority alternative at a one-sided significance level of 0.025 will be used. If the inferiority of CR rate of clofarabine is rejected, the superiority test will be performed at a one-sided 0.025 significance level.

Rev. 2/12 At each interim analysis, the study will be monitored for early stopping in favor of either superior OS on the clofarabine arm or inferior OS on the clofarabine arm in the context of the non-inferiority test of OS. Meanwhile, the study will also be monitored for early stopping in favor of an inferior CR rate on the clofarabine arm. In the event that at an interim analysis the criterion for inferiority of CR rates is met, but there is a trend towards superiority of survival, the DMC may decide to continue the study in spite of the inferiority of the CR rate.

As other secondary endpoints, we want to determine the effect of decitabine on disease free survival (DFS) as a maintenance therapy in comparison with observation. Also in this study, we want to evaluate the impact of consolidation with non-ablative conditioning and allogeneic hematopoietic stem cell transplantation with an HLA-identical sibling on overall survival in patients who achieve a 'morphologic leukemia-free state'.

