If criteria for early stopping given in Section [9.3](#) are not met, the final analysis will be performed when 507 non-allo non-decitabine patients have died, which is anticipated to occur 7 years after the study begins active accrual. A two-sided 95% confidence interval on the log hazard ratio (clofarabine/standard) will be provided based on the weighted analysis as previously described, with age (60 to 69 vs. over 70), therapy-related AML, and the presence of AHD at the time of diagnosis of AML as the stratification factors.

If the 95% confidence interval on the log hazard ratio lies entirely below $\log(1.12)$, the non-inferiority of clofarabine treatment will be accepted. This analysis will be conducted in two ways: (1) comparing the treatments based on treatment assignment received at randomization and censoring the allo transplant patients at the time of transplant; and (2) comparing the treatment based on actual treatment received and again censoring the allo transplant patients (the weighted analysis removing the effect of maintenance decitabine will be used for both). The results will be credible only if the two analyses are reasonably consistent.

If clofarabine turns out to be non-inferior to the standard therapy, a two-sided 97.5% confidence interval on the log hazard ratio (clofarabine/standard) will be provided for the superiority test of OS. If the 97.5% confidence interval lies entirely below $\log(1)$, then clofarabine will be considered superior to the standard treatment. A p-value for superiority based on the weighted analysis will be presented to allow assessment of the strength of the evidence. The superiority test will be based on the ITT (intention-to-treat) principle, including all randomized patients and censoring the allo transplant patients at the time of transplant.

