9.3 Interim Analyses of Primary Endpoint

Interim analysis of the study will be performed for all semi-annual DMC meetings beginning when approximately 25% of planned full information (126 events) has occurred. Table 1 gives the expected timing of the analyses and the expected number of events under the alternative at each interim analysis. Because of delays in initiation of accrual and delays in data submission and processing, it is likely the actual analysis time will be 6-12 months later.

The study will be monitored for early stopping in favor of either the alternative hypothesis of superior OS on the clofarabine arm or the null hypothesis of inferior OS on the clofarabine arm using the repeated confidence interval (RCI) methodology similar to that described by Jennison and Turnbull (124). At each interim analysis, a two-sided 95% RCI on the log hazard ratio

(clofarabine/standard) will be computed, using the partial likelihood estimate and their truncated O'Brien-Fleming critical points listed in Table 1. The partial likelihood estimate of log hazard ratio and its robust variance estimator will be obtained using the weighted analysis described in Section 9.2. Since we do not want to stop the trial and declare the inferiority or superiority of clofarabine unless the results are convincing, a hazard ratio of 1 is pre-specified. If at any of the interim analyses, the 95% confidence interval of the log hazard ratio lies entirely below $\log(1)$, we may consider stopping the trial for the superiority of clofarabine; if the 95% confidence interval lies entirely above $\log(1)$, the study may need to be stopped due to the inferiority of clofarabine.

Table 1: The Interim Analyses for the Primary OS Comparison

Real Time (Years)	Information Time	Events Under the alternative	Truncated O-F critical points
2.2	0.25	127	3.2905
2.7	0.34	175	3.2905
3.2	0.44	224	3.2905
3.7	0.54	274	2.9491
4.2	0.64	325	2.6418
4.7	0.74	377	2.4402
5.2	0.85	429	2.2623
5.7	0.92	465	2.1928
7.0	1.00	507	2.0974

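### OS superiority is allotted one-sided 0.0125, but Section 9.3 lets interim looks declare it on a 0.025 boundary, so the stated overall control at 0.025 is not assured

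*Combined protocol and SAP*

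**What the plan says.** Section 9.1 sets a hierarchy. OS non-inferiority is tested at one-sided 0.025. If it is shown, two further tests open: "superiority of OS and 30 day mortality rate will both be tested at a nominal level of 0.0125 (one-sided"). The paragraph ends: "The overall type I error rate of all three tests is still controlled at 0.025". Section 9.1 also places interim monitoring of OS "in the context of the non-inferiority test of OS".

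Section 9.2 applies the 0.0125 at the final analysis: "a two-sided 97.5% confidence interval on the log hazard ratio (clofarabine/standard) will be provided for the superiority test of OS". It does not say whether that interval is adjusted for the interim looks.

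Section 9.3 computes a two-sided 95% repeated confidence interval at each look, "using the partial likelihood estimate and their truncated O'Brien-Fleming critical points listed in Table 1". The reference value is a hazard ratio of 1, for this reason: "Since we do not want to stop the trial and declare the inferiority or superiority of clofarabine unless the results are convincing". When the whole interval at a look falls under log(1), the action given is: "we may consider stopping the trial for the superiority of clofarabine". Table 1 has eight interim rows and a final row.

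Section 9.4 specifies Fisher's exact test for 30-day mortality. Section 9.5 reports that Step 1 accrual was suspended at 727 patients because OS favored standard therapy.

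**The concern.** One claim, OS superiority, has two error levels in the plan: 0.0125 in Sections 9.1 and 9.2, and 0.025 in the only interim boundary that can lead to it. The split into two halves of 0.0125 is the stated basis for testing superiority and mortality within 0.025. If superiority can be declared early on the wider boundary, its half is overspent and the statement of overall control no longer follows. No section gives a 0.0125 interim boundary, says that a crossing supports non-inferiority only, or says at what level superiority is judged after a stop.

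**Working it through.** **Inputs.** Table 1 event counts: 127, 175, 224, 274, 325, 377, 429, 465, 507. Table 1 critical points c_k: 3.2905 (looks 1-3), 2.9491, 2.6418, 2.4402, 2.2623, 2.1928, and 2.0974 at the end. Margin 1.12 and alternative 0.86 (Section 9.2). 30-day mortality 10% (Section 9.4). Total 747 patients, taken as 374 and 373 per arm.

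**Method.** Information is I_k = events/4. At a hazard ratio of 1 the statistics Z_k (positive favoring clofarabine) are standard normal with correlation sqrt(I_j/I_k). Superiority error = P(some Z_k > c_k at looks 1-8, before any Z_j < -c_j) + P(no earlier stop and Z_9 > c_F). This was computed by recursive integration and checked by simulation.

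**Step 1: the plan's own figures.** The split adds up: 0.0125 + 0.0125 = 0.025. Table 1 as printed spends 0.02496 one-sided. A single superiority test at the end at z = 2.2414 has error 0.0125. Both levels are therefore right taken separately.

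**Step 2: superiority error when crossings count.** Cumulative crossing probability at looks 1-8 is 0.0005, 0.0008, 0.0011, 0.0023, 0.0051, 0.0092, 0.0149, 0.0193. The 0.0125 is passed by look 7.

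| How superiority is claimed | Error at hazard ratio 1 |
|---|---|
| Crossing is the claim; final z = 2.2414 (unadjusted 97.5%) | 0.0219 |
| Crossing is the claim; final z = 2.36 (adjusted 97.5%) | 0.0205 |
| Crossing plus unadjusted 97.5% check; final z = 2.2414 | about 0.021 |
| Crossing, then adjusted 97.5% repeated interval | about 0.006 |
| Crossings never used to claim superiority; final z = 2.2414 | 0.0125 |

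The unadjusted check helps little because Table 1's points at looks 1-7 (3.2905 down to 2.2623) already exceed 2.2414. It first binds at look 8 (2.1928).

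**Step 3: overall error.** Superiority and mortality are gated on non-inferiority. At a hazard ratio of 1 the final non-inferiority test passes with probability Φ(sqrt(507/4)·ln 1.12 − 2.0974) = Φ(1.276 − 2.097) = 0.206. One-sided Fisher's exact test at 0.0125 with 10% mortality has an attained size of about 0.009. The correlation between the OS and mortality statistics is not in the documents, so a range is shown, with a crossing taken as the claim:

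| Assumed correlation | Final interval unadjusted | Final interval adjusted |
|---|---|---|
| 0 | 0.0236 | 0.0222 |
| 0.2 | 0.0249 | 0.0235 |
| 0.31 | 0.0256 | 0.0243 |
| 0.385 | 0.0261 | 0.0248 |
| 0.5 | 0.0266 | 0.0254 |
| 0.65 | 0.0269 | 0.0257 |
| 0.8 | 0.0260 | 0.0249 |

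The total passes 0.025 at a correlation of about 0.2 (unadjusted) or 0.4 (adjusted). The largest excess is 0.0269 − 0.025 = 0.0019. If the final non-inferiority test used 1.96 rather than 2.0974, the maxima would be 0.0272 and 0.0260.

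As an illustration only, deaths by day 30 are also OS events. Ignoring the weighting, −(1−p)·ln(1−p)/sqrt(p(1−p)·507/747) gives 0.31 at p = 6.7% (the Section 9.2 survival model at one month) and 0.38 at p = 10%.

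**The case against.** The strongest defense is that monitoring and the superiority test are separate. Section 9.1 ties interim monitoring to the non-inferiority test, which does hold one-sided 0.025, and Table 1 spends exactly that. Section 9.2 then tests superiority afterwards at 97.5%. The Section 9.3 rule is permissive. A combined reading is possible: stop on the 95% repeated interval, then judge superiority on a 97.5% repeated interval at that look. Its error is about 0.006, well inside 0.0125.

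Much of this stands. Acting on a crossing does not by itself break the allotment, and a reader who infers that it must goes beyond the text. What remains is that the combined reading is not written down, while Section 9.3 speaks of stopping and declaring superiority against a hazard ratio of 1 on the 95% interval. The text is ambiguous, and the control statement fails to hold on its most direct reading.

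Two other stronger inferences should be resisted. Adding 0.0219 and 0.0125 to get 0.034 ignores both the non-inferiority gate and the conservatism of Fisher's test. Nor is the non-inferiority test inflated: an interval that excludes 1 from below also excludes 1.12.

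**Conclusion.** This is a minor inconsistency in multiplicity control, not an arithmetic slip. If an interim crossing is taken as the superiority claim, or is followed only by an unadjusted 97.5% interval, the superiority error is about 0.020 to 0.022 against 0.0125 allotted. Overall error for superiority plus 30-day mortality is then about 0.022 to 0.027.

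A reader might conclude that the plan breaches 0.025. The documents do not show that. The answer turns on the OS/mortality correlation, which is an assumption here, and on whether the final interval is adjusted, which the plan leaves open. With an adjusted final interval, both illustrative correlations stay just below 0.025. The supportable conclusion is that control at 0.025 is not assured, with any excess at most about 0.002. The figures rest on information proportional to events, a hazard ratio of 1, no mortality difference, and no allowance for the weighting in the primary analysis.

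The practical effect is small: Section 9.5 reports that OS favored standard therapy, so no clofarabine superiority claim is in prospect.

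**What to change.** State in Sections 9.2 and 9.3 that any OS superiority claim, interim or final, is judged on a 97.5% repeated confidence interval. With one-sided 0.0125 O'Brien-Fleming-type spending and Table 1's 3.2905 truncation, the critical points are about 3.29 at looks 1-4, then 3.17, 2.77, 2.57, 2.47 and 2.36. Keep the 95% repeated interval for inferiority and non-inferiority monitoring. This gives a superiority error of 0.0125 and an overall error of at most about 0.021.

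Otherwise, qualify the Section 9.1 sentence to say that overall control at 0.025 is not guaranteed when superiority is declared from a Section 9.3 crossing, and say whether the final 97.5% interval is sequentially adjusted.

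The cost is one column in Table 1 or one sentence. Under the first option, superiority power at a hazard ratio of 0.86 falls from about 35% (34% if the final interval was already adjusted) to about 28%.

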9.2 Primary Endpoint and Sample Size

The primary objective of this trial is to determine the effect of clofarabine on overall survival in comparison with standard therapy. The primary endpoint is overall survival (OS). OS is defined as the time between randomization and death from any cause. Patients last known to be alive at the time of an analysis will be censored.

The primary comparison of OS will be based on the treatment assignment received at randomization. To reduce potential bias of the primary comparison from the alloSCT arm, the patients will be censored at the time of allogeneic transplant for the primary analysis. Due to the potential confounding by maintenance therapy on the induction comparison, a weighted analysis (weighted Cox regression) (121,122,123) will be used for the primary analysis. Let π denote the actual proportion randomized to the observation arm of all patients entering on maintenance randomization. In the weighted analysis, patients who do not enter maintenance randomization get weight 1; Observation maintenance arm patients get weight $1/\pi$. Decitabine maintenance arm patients get weight 0. Thus, patients on the observed maintenance arm represent themselves as well as the response of $(1/\pi - 1)$ similar patients in the decitabine maintenance arm. A robust variance estimator that correctly accounts for the weights will be used in this setting.

Because long-term cures have been observed in previous studies with the same patient population, we assume a cure rate mixture distribution for the standard arm, with the distribution on the clofarabine arm given by a proportional hazards shift from the standard arm, to calculate power. Based on a previous ECOG study, E3999, we assume that the long-term cure rate in the standard treatment arms will be 10% and median survival among the non-cured group will be about 9 month, i.e., the survival model for the standard treatment arm $S_0(t) = 0.1 + 0.9 \exp(-t^* \log(2)/9)$. The study team would consider clofarabine to be acceptable if the long-term cure rate in the clofarabine arms will be no lower than 8% and median survival among the non-cured group will be no less than 8 months, which is approximately a less than 12% increase in hazard rate. Therefore, our null hypothesis is that the hazard ratio for clofarabine/standard is no less than 1.12. The alternative is that the hazard ratio for clofarabine/standard is no more than 0.86. The non-inferiority of clofarabine will be tested at a one-sided significance level of 0.025.

We assume that 8% of those patients will undergo allogeneic transplant. We also assume that 25% of patients who do not receive allogeneic transplant go through the second randomization. Adjusted for the sequential monitoring described below and based on the weighted analysis previously described, with 685 patients, the study will have approximately 80% power to reject the null hypothesis of inferiority of clofarabine at the one-sided significance level of 0.025 under the alternative above, assuming 5 years of accrual and 2 years of follow-

up after the completion of accrual. The size and power of the study will not be affected even if the proportions of patients receiving maintenance are imbalanced between the induction arms. The full information needed is 507 events. This information is the expected number of deaths among the non-allo non-decitabine patients under the alternative. Deaths on the decitabine maintenance arm do not contribute information to this comparison. Since the allo transplant patients are censored at the time of transplant, they do not contribute events. Therefore, the overall sample size was increased by 1/(1-0.08), around 9%, to make up for the loss of information. A total accrual of 747 patients is planned for this study.

If criteria for early stopping given in Section [9.3](#) are not met, the final analysis will be performed when 507 non-allo non-decitabine patients have died, which is anticipated to occur 7 years after the study begins active accrual. A two-sided 95% confidence interval on the log hazard ratio (clofarabine/standard) will be provided based on the weighted analysis as previously described, with age (60 to 69 vs. over 70), therapy-related AML, and the presence of AHD at the time of diagnosis of AML as the stratification factors.

If the 95% confidence interval on the log hazard ratio lies entirely below $\log(1.12)$, the non-inferiority of clofarabine treatment will be accepted. This analysis will be conducted in two ways: (1) comparing the treatments based on treatment assignment received at randomization and censoring the allo transplant patients at the time of transplant; and (2) comparing the treatment based on actual treatment received and again censoring the allo transplant patients (the weighted analysis removing the effect of maintenance decitabine will be used for both). The results will be credible only if the two analyses are reasonably consistent.

If clofarabine turns out to be non-inferior to the standard therapy, a two-sided 97.5% confidence interval on the log hazard ratio (clofarabine/standard) will be provided for the superiority test of OS. If the 97.5% confidence interval lies entirely below $\log(1)$, then clofarabine will be considered superior to the standard treatment. A p-value for superiority based on the weighted analysis will be presented to allow assessment of the strength of the evidence. The superiority test will be based on the ITT (intention-to-treat) principle, including all randomized patients and censoring the allo transplant patients at the time of transplant.

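### The maintenance weights of 0 and 1/π carry no start date in Section 9.2, so as written they act from first randomisation and add avoidable variance to the primary overall survival comparison

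*Combined protocol and SAP*

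**What the plan says.** Section 9.2 defines overall survival from first randomisation and censors transplanted patients at transplant. Because maintenance could confound the induction comparison, the primary analysis is a weighted Cox regression with a robust variance. Patients who never enter the maintenance randomisation have weight 1, and observation patients have 1/π, where π is the actual proportion of entrants allocated to observation. For the remaining patients, "Decitabine maintenance arm patients get weight 0". No sentence makes a weight depend on follow-up time.

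The sizing paragraph adds that "Deaths on the decitabine maintenance arm do not contribute information to this comparison" and gives full information as 507 deaths. The null is that "our null hypothesis is that the hazard ratio for clofarabine/standard is no less than 1.12", and "The alternative is that the hazard ratio for clofarabine/standard is no more than 0.86". The test is one-sided at 0.025, and "with 685 patients, the study will have approximately 80% power to reject the null hypothesis of inferiority of clofarabine".

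Section 9.3 carries the scheme into every interim look: the partial likelihood estimate and "its robust variance estimator will be obtained using the weighted analysis described in Section 9.2". Section 9.6 uses it again, as a supplement to a stratified log-rank test.

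**The concern.** Maintenance can affect survival only after the second randomisation, which follows induction, two consolidation cycles and restaging. Until then a future decitabine patient has received exactly the assigned induction and consolidation, and is as informative about the induction comparison as anyone else at risk. A weight fixed for all of follow-up takes that patient out of the early risk sets and lets an observation patient stand in for two. Over those months there is no confounding to remove, so the only effect is noise.

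At stake is the precision of the primary hazard ratio, and through it the power of the non-inferiority test. A larger variance also widens the interim repeated confidence intervals and lowers superiority power, but the size of those two effects was not calculated.

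**Working it through.** **Inputs from the documents.** Section 9.2: "long-term cure rate in the standard treatment arms will be 10% and median survival among the non-cured group will be about 9 month", so S0(t) = 0.1 + 0.9·exp(−t·ln 2/9) with t in months; margin 1.12; alternative 0.86; 685 non-transplant patients; 25% entering the second randomisation; 5 years of accrual and 2 of follow-up. Table 1: final critical value 2.0974. Section 9.5: 120 of 727 (16.5%) actually entered.

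**Assumptions.** Allocation at the second randomisation is 1:1 (Section 9.8 assumes 86 and 86), so 1/π is about 2. Time to the second randomisation is not stated. An outcome marrow at day 28–56 (7.1), two consolidation cycles at 4–6 week intervals (5.1.6) and maintenance within 60 days of count recovery (3.2.8) suggest about 3 to 8.5 months. Entrants' prognosis relative to other survivors is not given and was varied.

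**Step 1: the plan's own figures.**
- Under uniform accrual with analysis at 7 years, the mean probability of death under S0 and S0^0.86 is 0.848. Non-decitabine deaths: 685 × 0.875 × 0.848 ≈ 508.5, against 507 stated.
- Power: Φ(√(507/4) × ln(1.12/0.86) − c) = Φ(11.258 × 0.2641 − c) = Φ(2.974 − c). This is 81.0% at c = 2.0974 and 84.5% at c = 1.96, against about 80% stated.

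The stated figures reproduce, using a plain event count.

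**Step 2: what the start date changes.** An entrant cannot die before the second randomisation. Decitabine-arm deaths therefore have weight 0, and observation deaths weight 1/π, under either scheme. Only the risk-set sums before the second randomisation differ. For an entrant the expected fixed weight is π × (1/π) + (1 − π) × 0 = 1, so those sums are right on average and no bias arises. The variance of that weight is 1/π − 1, about 1 when π = 0.5; with weight 1 until the second randomisation it is 0. That is the avoidable noise.

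**Step 3: size.** Paired simulation (12,800 runs per scenario): 685 patients, the 9.2 survival model, hazard ratio 0.86, weighted Cox with robust variance. Fixed weights are compared with weights that start at the second randomisation. Power is at 2.0974.

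| Entry, months | Entrants | Share entering | Fixed | Start-stop | Gain, points |
|---|---|---|---|---|---|
| 3.5–5 | like other survivors | 25% | 77.2% | 78.1% | 0.9 |
| 4–6 | like other survivors | 25% | 76.8% | 77.9% | 1.1 |
| 5–7 | like other survivors | 25% | 76.0% | 77.7% | 1.8 |
| 7–9 | like other survivors | 25% | 75.5% | 78.2% | 2.7 |
| 4–6 | mildly better | 25% | 72.9% | 76.4% | 3.4 |
| 5–7 | mildly better | 25% | 72.6% | 76.2% | 3.6 |
| 3.5–5 | markedly better | 25% | 70.6% | 74.3% | 3.6 |
| 5–7 | markedly better | 25% | 65.6% | 72.6% | 7.0 |
| 5–7 | like other survivors | 16.5% | 79.4% | 80.4% | 0.9 |
| 5–7 | mildly better | 16.5% | 76.2% | 78.9% | 2.7 |

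Gains come from unrounded results. Worked example, entry at 5–7 months, mildly better, 25%: the average robust standard errors are 0.0976 (fixed) and 0.0936 (start-stop). The variance reduction is 1 − (0.0936/0.0976)² = 8.0%. Power is Φ((0.1133 + 0.1504)/0.0976 − 2.0974) = 72.7% and Φ((0.1133 + 0.1503)/0.0936 − 2.0974) = 76.4%, in line with the simulated rejection rates.

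Further paired simulations with other entry windows and prognosis models put the variance reduction at 1–15% and the gain at about 1 to 8 points. The smallest single result was 0.5, in a 2,500-trial run with entry at 4–6 months and entrants like other survivors.

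**Step 4: validity.** The mean log hazard ratio was about −0.151 (ln 0.86 = −0.151) under both schemes. In a separate simulation of 4,000 trials per setting, both rejected 2.6% of the time at a true hazard ratio of 1.12, using 1.96.

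**The case against.** The strongest reply is that this is a choice between two valid estimators of the same quantity, and that the plan says it was sized on the weighted analysis. That stands: the loss is relative to a better use of the same data, and the plan never promised start-stop weights.

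It is also fair that the fixed reading is inferred. Section 9.2 says nothing about time and cites three methods papers for the weighting; if one of them defines time-dependent weights, the plan does not repeat it. The sentence about decitabine deaths and the 507 count do not settle the question, since those deaths have weight 0 either way. The reading rests on the weight definitions alone.

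The size depends on unknowns. With early entry and entrants like other survivors it is about one point.

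Several stronger inferences are tempting, and the documents do not support them:
- That the primary estimate is biased or the type I error inflated. Steps 2 and 4 show neither.
- That deaths are thrown away. Only time at risk before the second randomisation is affected.
- That this accounts for the gap between the stated power of about 80% and the simulated 76–77% under fixed weights with entrants like other survivors. Start-stop weights recover only part of it; the rest reflects weighting after the second randomisation, which the event-count formula does not charge for.
- That the interim result favouring standard therapy is in doubt. Both schemes estimate the same hazard ratio.

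**Conclusion.** The point holds as an avoidable loss of precision in the primary analysis as written. At 2.0974 and 25% entry, the cost in non-inferiority power is about 1 to 3 points if entrants resemble other survivors and about 2 to 8 if their prognosis is better. Better prognosis is plausible, because Section 3.2.8 requires continuing CR or CRi and performance status 0–2 after two consolidation cycles. At the observed 16.5% entry rate the two simulated cases gave 0.9 and 2.7 points.

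These figures assume 1:1 allocation, the 9.2 survival model and entry at roughly 3.5 to 9 months. They describe the final look alone and ignore stopping at earlier looks. Section 9.5 limits the practical benefit: Step 1 accrual was suspended in February 2015, after 727 of 747 patients, on an interim survival analysis. What remains is a tighter final survival estimate and a tighter supplementary analysis in 9.6.

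**What to change.** In Section 9.2, state that every patient has weight 1 from randomisation to the date of the second randomisation, and that from that date observation patients have weight 1/π and decitabine patients weight 0, with robust variance clustered on patient. Carry the same definition into Section 9.3 and the supplementary weighted analysis in 9.6.

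Because outcome data had been reviewed before this version, do not silently replace the estimator. Keep the prespecified fixed-weight result, report the start-stop version beside it, and label it as added later.

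The cost is SAP wording and start-stop programming. The second-randomisation date is already recorded at Step 3, so no new data are needed, and the estimand does not change.
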